## Background and Significance

Platelet transfusion is commonly provided to patients with moderate or severe TBI who are on antiplatelet medications. Evidence suggests that patients on antiplatelet medications may have worse outcomes following TBI. Current literature has not demonstrated major outcome improvements in those patients who receive platelet transfusion. This lack of significant benefit may be due to insufficient dosing or due to the poor hemostatic function of standard care room temperature platelets. Studying the potential benefits of Cold Stored Platelet transfusion in the TBI population will provide needed direct comparison of room temperature and cold stored platelet transfusion which is unable to occur in patients with hemorrhagic shock, who may require large volumes of red blood cells and plasma concomitantly with platelet transfusion.

By providing Cold Stored Platelets in an urgent release fashion following injury, a potentially superior hemostatic agent is given early, closer to the time of injury. The current pilot trial was designed to determine the feasibility, efficacy and safety of urgent release cold stored platelets as compared to standard care in TBI patients requiring platelet transfusion. There are no high-level data which appropriately characterize the urgent release use of cold stored platelets out to 14 days or their function over that time period as compared to standard room temperature platelets. These results will be able to inform future large randomized clinical trials allowing the most appropriate injured population, inclusion criteria, and primary outcome to be selected and utilized.

## Study Design/Setting

The current proposed pilot study will be a 3-year, single center, open label, randomized trial utilizing a level-1 trauma center at the University of Pittsburgh and will randomize approximately 100 patients with TBI.

Study Population: Traumatic brain injured patients with a non-penetrating injury requiring platelet transfusion.

## Inclusion Criteria:

Patients with traumatic brain injury, defined by presence of potential progressive intracranial injury on CT scan imaging, at significant risk for urgent neurosurgical procedure as determined by neurosurgical evaluation, who meet at least one of the following:

- a) History or indication of pre-injury antiplatelet agent use
- b) Need for platelet transfusion per standard practice

Exclusion Criteria:

1. Wearing NO CriSP opt out bracelet
2. Hypotension in ED (SBP< 90 mmHg)
3. Age > 89 or < 18 years of age
4. Penetrating injury
5. Prisoner
6. Pregnancy
7. Going to operating room for non-neurosurgical intervention in first 60 minutes
8. Platelet transfusion contraindicated per care team (for example, recent vascular stent, embolic stroke, intracranial and/or vascular lesions)
9. Objection to study voiced by participant or family member in Emergency Department
10. Currently on therapeutic anticoagulant in addition to aspirin and/or clopidogrel (e.g. warfarin, direct-acting oral anticoagulants)

Screening and enrollment: Participants will be identified prospectively, within the 2-hour period after CT scan in the ED, by research personnel that are trained and familiar with the inclusion and exclusion criteria. An additional CT scan may be performed as standard care at UPMC Presbyterian for those participants being transferred to UPMC Presbyterian after the injury is identified at an outside facility. Those subjects who arrive more than 2 hours after initial scan at the outside hospital will still be considered for enrollment. Patients who meet all inclusion and no exclusion criteria will be randomized to CSPs or standard of care based upon the predetermined randomization assignment. Patients who meet all inclusion and no exclusion criteria will be randomized to CSPs or standard of care based upon the predetermined randomization assignment.

Capacity to provide informed consent will be assessed prior to randomization and will primarily be determined by Glasgow Coma Scale (GCS). Potential subjects with a GCS of less than 15 will be considered unable to consent. Potential subjects with a GCS of 15 will undergo a GOAT assessment, performed by a study investigator or neurosurgery CRC. A score of 74 or below will be considered unable to consent. For subjects that are determined to be unable to consent, assent will be obtained when applicable. The study team will also attempt to identify an appropriate LAR to provide prospective informed consent. If a LAR is identified within the 2-hour period after initial CT scan in the ED, this individual will be approached for proxy consent. If not, the patient will be enrolled under EFIC. If a potential subject has a GCS of 15 and scores 75 or above on the GOAT, we will presume s/he is capable of providing direct informed consent and will seek to obtain informed consent via a physician investigator.

VerifyNow Measurements: When feasible, VerifyNow-Aspirin and VerifyNow-P2Y12 measurements for patients with a history of aspirin and/or clopidogrel, respectively, may be performed prior to platelet transfusion and for response monitoring following initial platelet transfusion. However, need for platelet transfusion will be determined by neurosurgical and/or trauma surgery recommendations. VerifyNow measurements will only be obtained when feasible. Measurement cut points for determining platelet inhibition will follow manufacturer guidelines <https://www.werfen.com/na/en/verifnow> .

**Study Intervention:**

**Study Intervention Arm:** Patients randomized to the intervention arm will receive an early infusion of urgent release cold stored platelets (CSP) once the patient is determined to meet all inclusion and no exclusion criteria. When clinically feasible, patients will undergo VerifyNow Aspirin or P2Y12 testing following initial platelet transfusion. Those patients who have not increased their respective ARU or PRU measurements to levels consistent with no drug effect (ARU > 550; PRU > 220), or who have another clinical indication for additional platelet transfusion, may undergo a second CSP infusion.

CSP infusion will occur once IV access is obtained irrespective of location. CSP infusion should be initiated first when possible but can be infused concomitantly with other transfusion requirements including packed red blood cells, plasma, or whole blood per institutional standard care. The administration will be begun by clinical staff.

**Standard Care Arm:** Patients randomized to the standard care arm will receive room temperature (RT) platelet transfusion per standard care at the University of Pittsburgh once the patient meets all inclusion and no exclusion criteria. When clinically feasible, patients will undergo VerifyNow Aspirin or P2Y12 testing following initial platelet transfusion. Those patients who have not increased their respective ARU or PRU measurements to levels consistent with no drug effect (ARU > 550; PRU > 220), or who have another clinical indication for additional platelet transfusion, may undergo a second RT platelet infusion.

**Randomization and Masking:** Individual patients determined to meet all inclusion and no exclusion criteria in the emergency department will be randomized and assigned according to a 1:1 ratio to CSP infusion or standard care using a permuted block design with variable block sizes of 4 and 6. The arm assignment will be provided in real time at the individual patient level by accessing an electronic randomization system. Backup envelopes containing randomization assignments will be available by contacting the Data Coordinating Center should there be any issues or failure of the electronic randomization system. Trauma and Neurosurgical attending and ED physicians will not be masked to treatment assignment as the study intervention is a blood product and full traceability is required. Arm assignment will be concealed to all outcome assessors performing the GOSE during follow-up.

In order to facilitate the early administration of platelets, randomization of eligible patients will occur within 2 hours of diagnosis of TBI via CT scan in the ED.

The study team may call the participant to check on their status after 30 days and again after 6 months. If the participant is discharged to another facility, they may be contacted at that facility for an update of their condition.

If we are unable to get in touch with the participant or with the facility they were discharged to, we will check survival status on a public access database using personal identifiers such as name, date of birth, and social security number.

**Follow-up procedures:** Galveston Orientation and Amnesia Test (GOAT): We will obtain the GOAT score prior to discharge and the calculated score per standard methods. (Figure 1) GOAT is a 10-item questionnaire used to quickly assess post-traumatic amnesia following head injury. The GOAT is read orally to the patient and may be easily administered at the bedside. The total score accounts for orientation of person, place, and time, and recollection of events pre and post- injury. Cutoff scores are available to identify abnormal, borderline, and normal orientation and it will additionally determine if a participant is able to provide continuing participation consent after the process of EFIC.

**Figure 1:**

**The Galveston Orientation and Amnesia Test (GOAT)**

Question	Error score	Notes
What is your name?	/ 2	Must give both first name and surname.
When were you born?	/ 4	Must give day, month, and year.
Where do you live?	/ 4	Town is sufficient.
Where are you now?		
(a) City	/ 5	Must give actual town.
(b) Building	/ 5	Usually in hospital or rehab center. Actual name necessary.
When were you admitted to this hospital?	/ 5	Date.
How did you get here?	/ 5	Mode of transport.
What is the first event you can remember after the injury?	/ 5	Any plausible event is sufficient (record answer)
Can you give some detail?	/ 5	Must give relevant detail.
Can you describe the last event you can recall before the accident?	/ 5	Any plausible event is sufficient (record answer)
What time is it now?	/ 5	1 for each half-hour error, etc.
What day of the week is it?	/ 3	1 for each day error, etc.
What day of the month is it? (i.e. the date)	/ 5	1 for each day error, etc.
What is the month?	/ 15	5 for each month error, etc.
What is the year?	/ 30	10 for each year error.
Total Error:		
100 - total error		Can be a negative number.

76-100 = Normal

66-75 = Borderline

< 66 = Impaired

**Extended Glasgow Outcome Scale (6 months-GOSE):** The GOSE score will be obtained at 6 months (+/- 1month) by home survey or direct patient contact, whichever is feasible. For those participants who were unable to consent at discharge, the GOAT will be administered to assess their ability to provide direct consent, prior to the administration of the GOSE. When the assessment is done by phone, the verbal consent of participants who have regained the ability to consent will be obtained to allow the GOSE to be completed. The score can characterize 6-month functional status into 8 well defined categories as shown in (Figure 2).

**Figure 2:**

1	Death	D
2	Vegetative state	VS
3	Lower severe disability	SD -
4	Upper severe disability	SD +
5	Lower moderate disability	MD -
6	Upper moderate disability	MD +
7	Lower good recovery	GR -
8	Upper good recovery	GR +

**Study Drug/Intervention:** Up to 2 cold stored apheresis units issued at the University of Pittsburgh will represent the CSP intervention. The volume of each unit will be approximately 200-300 mls and each will be stored in an FDA monitored approved refrigerator at 1-6 degrees Celsius for up to 14 days from preparation.

Please refer to the Investigator Brochure for additional details regarding CSP preparation, labeling, storage, dosing, and administration.

**Study risks and benefits:** Risks associated with blood component transfusion include infection, allergic reaction, fever, and respiratory distress. Additional risks associated with platelet transfusion include bacterial contamination, platelet alloimmunization, and hemolysis. Due to the higher activation in CSP as compared to RTP, there is a potential for increased risk of thrombotic complications. A detailed list of risks associated with the transfusion of platelets is included in the Investigator Brochure.

## Outcomes

**Primary Outcome:** The primary outcome for this pilot trial will be feasibility. Secondary performance and feasibility outcomes will include the proportion of eligible patients that can be randomized, 2) the proportion of eligible patients who are enrolled in the trial, 3) proportion of enrolled patients which adherence to the study protocol, and 4) proportion of enrolled patients who complete study follow-up.

**Secondary Outcomes:** Our principle secondary clinical outcome for the proposal will be 6-month Extended Glasgow Outcome Scale (GOS-E). Additional secondary outcomes will include 24-hour mortality, in-hospital mortality, need for craniectomy/craniotomy, need for ICP monitoring, TBI progression based upon serial CT imaging in initial 24 hours, Galveston Orientation and Amnesia Test (GOAT score) at discharge, incidence of allergic/transfusion reaction, incidence of transfusion related acute lung injury (TRALI), measurements of platelet hemostatic function, and incidence of thromboembolic events.

## Secondary Outcome Definitions:

**Extended Glasgow Outcome Scale (6 months-GOSE):** The GOSE score will be obtained at 6 months +/- 1 month by phone survey or direct patient contact, whichever is feasible. Patients will be consented for this contact outcome. The score can characterize 6-month functional status into 8 well defined categories.

**24-hour and In-Hospital Mortality:** 24-hour and in hospital mortality will be recorded from the time of arrival. Over the first 24 hours we will document and record the time of death in hours, while after the 24-hour time period, we will document and record the time of death in days from arrival.

**TBI progression in 24 hours:** Common Data Elements (CDE) for CT scan indicators of hemorrhage progression will be utilized.

<https://www.commondataelements.ninds.nih.gov/Traumatic%20Brain%20Injury>

**Galveston Orientation and Amnesia Test (GOAT):** We will obtain the GOAT score prior to discharge and the calculated score per standard methods. GOAT is a 10-item questionnaire used to quickly assess post-traumatic amnesia following head injury. The GOAT is read orally to the patient and may be easily administered at the bedside. The total score accounts for orientation of person, place, and time, and recollection of events pre and post- injury. Cutoff scores are available to identify abnormal, borderline, and normal orientation and it will additionally determine if a participant is able to provide continuing participation consent.

**Allergic/Transfusion reaction:** Any transfusion complication in the ED and OR/IR setting will be monitored. As the intervention is specific to the early phase of care setting and since transfusion complications are temporally related to the specific transfusion, all transfusion related complications will be assessed during the initial 24 hours from arrival and recorded.

**Transfusion Related Acute Lung Injury (TRALI):** TRALI will be defined as the occurrence of ARDS (mild;  $\text{PaO}_2/\text{FIO}_2 \leq 300 \text{ mm Hg}$ ) that occurs within 6 hours of transfusion of a blood product. There may be multiple blood products transfused to the patient including PRBCs, plasma in addition to platelets during the early resuscitation period. The causal factor that results in TRALI may be unable to be determined but will be recorded.

**Platelet Hemostatic Function:** Once randomized, blood sampling for platelet hemostatic function prior to platelet transfusion irrespective of arm assignment will be performed if clinically feasible. Following each platelet transfusion, further assessment of platelet hemostatic function may be performed (up to 2 times). Platelet hemostatic function will be assessed by TEG analysis and TEG with platelet mapping. Whole blood aggregometry and flow cytometry will be performed when feasible across both arms.

**Thromboembolic events:** Pulmonary embolism, venous thrombosis, or arterial thrombosis that occurs during the primary admission hospital stay will be documented for all enrolled patients. Radiographic confirmation via CT imaging, transthoracic or trans-

esophageal echo, or ventilation/perfusion scanning will be required. Presumed or clinical suspicion for an embolic event that is unable to be verified radiographically will also be documented.

**Severity Stratification:** TBI characteristics will be recorded and based upon CT imaging results (classification: subarachnoid, subdural, intracerebral hemorrhage, epidural, +/- shift, multifocal) and TBI severity will be characterized by presenting GCS, Abbreviated Injury Severity (AIS) coding and Rotterdam CT scores.

**Predefined Subgroups:** Predefined subset analyses for the TBI cohort will be performed looking at 1) patients who did or did not receive a craniectomy/craniotomy, 2) patients who did or did not require ICP monitoring, 3) patients arrived from the scene of injury versus those brought from a referral hospital; 4) patients with a pre-injury history of aspirin use as compared to clopidogrel use; 5) CSPs with shelf time of 1 to 7 days as compared to 8 to 14 days. It is recognized that the study is not appropriately powered for these subgroup comparisons and the results and conclusions formulated from these subgroup analyses will be considered exploratory in nature and will not be used as a basis for treatment recommendations.

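### Transfusion reactions are counted for 24 hours from arrival rather than from each platelet unit, so late units get a short window, or none, for this one outcome.

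*Combined protocol and SAP*

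**What the plan says.** All references are to the combined protocol and SAP.

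- **Clock.** Under Secondary Outcome Definitions, the Allergic/Transfusion reaction entry states that "all transfusion related complications will be assessed during the initial 24 hours from arrival and recorded". The reason given in the same sentence is that the intervention belongs to the early phase of care and that "transfusion complications are temporally related to the specific transfusion".
- **Setting.** The entry opens with "Any transfusion complication in the ED and OR/IR setting will be monitored". No ward or ICU is named.
- **First unit.** Under Study Intervention, a patient assigned to cold stored platelets (CSP) "will receive an early infusion of urgent release cold stored platelets (CSP) once the patient is determined to meet all inclusion and no exclusion criteria". The control arm receives room temperature (RT) platelets under local standard care, on the same eligibility trigger. CSP is to be infused wherever the patient is once there is IV access. The only time limit is on randomization, in the text after Randomization and Masking: "randomization of eligible patients will occur within 2 hours of diagnosis of TBI via CT scan in the ED".
- **Second unit.** A control patient whose platelet test has not corrected, or who has another clinical reason, "may undergo a second RT platelet infusion". The CSP arm has matching wording. Neither arm has a time limit.
- **Analysis.** Under Analysis for Clinical Outcomes, binary outcomes are compared as simple proportions by chi-square test, followed by logistic regression adjusted for baseline GCS. Time at risk is not considered.

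**The concern.** The definition gives a reason for following each transfusion and then follows the patient from arrival instead. Time already spent in hospital before a unit is given is taken off that unit's observation. A reaction to a late second unit, or one that appears on the ICU or ward, may not enter the endpoint.

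Safety is one of the trial's stated aims, and the clinical hypothesis expects a similar reaction rate in the two arms. Reactions that go uncounted lower both rates and make a real difference harder to see. The trial is open label, and only the GOSE assessors are stated to be masked, which is a further reason for an unambiguous window.

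**Working it through.** The documents give no expected reaction rate, margin or power for this outcome, and no times from arrival to transfusion. There is no figure of the plan's own to reproduce. The window arithmetic is exact. Everything about timing, onset and event rate below is an assumption.

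**Step 1. Observation left after a unit.** With t the hours from arrival to the unit, observation = max(0, 24 - t).

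| t (h, assumed) | Observation for this outcome (h) |
|---|---|
| 3 | 24 - 3 = 21 |
| 6 | 24 - 6 = 18 |
| 12 | 24 - 12 = 12 |
| 18 | 24 - 18 = 6 |
| 20 | 24 - 20 = 4 |
| 24 or later | 0 |

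This shortening needs no difference between arms.

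**Step 2. Share of reactions captured.** Assume that the time from transfusion to onset is exponential with median m, so F(u) = 1 - 2^(-u/m). Of the reactions that would appear within 24 hours of the unit, the share captured is F(24 - t)/F(24). If CSP units are given at one time and RT units at another, and the true risks are equal, the false CSP:RT ratio is the ratio of the two shares.

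| CSP time vs RT time (assumed) | m = 1 h | m = 4 h | m = 8 h |
|---|---|---|---|
| 3 h vs 3 h | 1.00 | 1.00 | 1.00 |
| 3 h vs 5 h | 1.00 | 98.9% / 97.8% = 1.01 | 95.8% / 92.3% = 1.04 |
| 3 h vs 9 h | 1.00 | 98.9% / 94.0% = 1.05 | 95.8% / 83.1% = 1.15 |
| 12 h vs 18 h | 100% / 98.4% = 1.02 | 88.9% / 65.7% = 1.35 | 73.9% / 46.3% = 1.60 |

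**Step 3. Size in events.** Take an assumed reaction rate of 5% and the planned 50 patients per arm, so 50 × 0.05 = 2.5 expected reactions per arm. With the slowest onset (m = 8 h):

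- At 3 h vs 5 h, the difference in capture is 2.5 × (0.958 - 0.923) = 0.09 of an event.
- At 12 h vs 18 h, it is 2.5 × (0.739 - 0.463) = 0.69 of an event, and only if every unit in each arm were that late.

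**Step 4. Other safety windows in the plan.**

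| Outcome | Window |
|---|---|
| Allergic/transfusion reaction | 24 h from arrival |
| TRALI | 6 h from transfusion |
| Thromboembolic events | Primary admission |
| Related adverse events | Enrollment to end of participation |

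Only the first is tied to arrival. TRALI, defined in the next entry, already runs from the transfusion.

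**The case against.** The strongest defence is that the arrival clock is a deliberate choice. It is the same for every randomized patient, it matches the mortality clock, and it suits an intervention meant for early care. Most first units should follow soon after randomization, and Step 2 shows that almost nothing is then lost. That stands for early first units. It does not cover second units, for which the plan sets no time limit.

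Three stronger readings are tempting, and the documents do not support them.

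- **RT will look safer because it starts later and is watched for less time.** CSP is described as early and urgent release, and RT as standard care, so a gap is possible. But both arms share the eligibility trigger, the randomization limit and the second-unit wording, and no transfusion times are given. Both the gap and its direction are inference.
- **Safety follow-up as a whole is cut short.** Only this outcome uses the arrival clock. The section Assessing and Reporting Adverse Events provides for related events through the end of participation, so a late reaction need not go unrecorded. That section does not say that such records feed the comparison of reaction rates, so the gap in the endpoint remains.
- **A unit at hour 20 loses part of its TRALI window.** TRALI is a separate outcome with its own 6 hours from transfusion. The word all in the reaction entry creates at most a wording overlap.

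A window from the first unit to 24 hours after the last would also be a poor remedy. It lengthens with a second unit, which depends partly on the response to the first. It is undefined for randomized patients who receive no study platelets, although the Non-adherence section keeps them in the analysis by intention to treat.

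**Conclusion.** The point holds in a limited form. The clock does not fit the plan's own rationale, and the named settings do not cover every place where platelets may be given. A unit given t hours after arrival has 24 - t hours of observation for the reaction outcome, and none from hour 24.

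For first units given soon after randomization the effect is negligible. For late units with slower-onset reactions it can be material: the false ratio reaches 1.35 to 1.60 at 12 h vs 18 h with median onset of 4 to 8 h. Those figures rest on assumed transfusion times that differ by arm and on exponential onset. With equal timing there is no false difference, only undercounting of reactions to late units in both arms.

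Severity is minor. The outcome is secondary and has no power calculation, in a 100-patient pilot whose primary outcome is feasibility. No sample size, alpha or primary conclusion depends on it.

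**What to change.** Change the definition of the Allergic/Transfusion reaction outcome as follows:

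1. Count reactions during, and in a fixed 24 hours after, each study platelet unit (CSP or RT), in any care location and identically in both arms.
2. Record the start and end time of every study unit.
3. Keep all randomized patients in the denominator. A patient with no study unit counts as having no study-platelet reaction.
4. Report the number of units per patient by arm, and reactions per unit alongside the patient-level proportion.
5. Keep the count of all transfusion complications in the first 24 hours from arrival as a supporting summary, so that reactions to other products are still described.
6. State that TRALI and related adverse events keep their own windows.

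Each unit then gets the same 24 hours whatever its timing.

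The cost is new outcome and case report form wording, and slightly longer chart review for patients with late units. One limitation remains: patients given two units have more total observed time. The per-unit report makes this visible but does not remove it.
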